6.2 Exclusion criteria

1. Previous major knee surgery
2. Other significant disabling problems from the muscular-skeletal system than in the knees
3. Obese patients where obesity is severe enough to affect subject's ability to perform activities of daily living (body mass index, kg/m²: BMI \geq 35).
4. Patients with active or suspected infection.
5. Patients with malignancy – active malignancy.

6. Patients with severe osteoporosis, Paget's disease, renal osteodystrophy.
7. Patients immunologically suppressed, or receiving steroids in excess of physiologic dose requirements.
8. The patient has a neuromuscular or neurosensory deficit which would limit the ability to assess the performance of the device or the patient has a neurological deficit which interferes with the patient's ability to limit weight bearing or places an extreme load on the implant during the healing period.
9. Female patients planning a pregnancy during the course of the study.
10. Patients with systemic or metabolic disorders leading to progressive bone deterioration.
11. Patients, who as judged by the surgeon, are mentally incompetent or are unlikely to be compliant with the prescribed post-operative routine and follow-up evaluation schedule.
12. Patients with other severe concurrent joint involvements, which can affect their outcome.
13. Patients with other concurrent illnesses, which are likely to affect their outcome such as sickle cell anaemia, systemic lupus erythematosus or renal disease requiring dialysis.
14. Patients under the protection of law (e.g. guardianship).

7. Prostheses

All components of the knee systems used in this study are CE marked and have been approved for sale and use throughout Europe. All prostheses have chrome-cobalt femoral components and tibial trays. The polyethylene is relatively unconstrained. Both Triathlon and Duracon tibial trays have delta-shaped stems. When required a cemented polyethylene patellar component will be used.

Sub-studies

- a) The prostheses inserted will be the Duracon total knee and the Triathlon total knee. Both prostheses will be Cruciate Retaining design.
- b) The second part of the study will include the Triathlon total knee in Cruciate Retaining (CR) and Posterior Stabilized (PS) version.
- c) Triathlon PA (hydroxyapatite on a porous surface) and Triathlon Press-fit (porous coated), both in Cruciate Retaining design. The in-growth surface for both the femoral and the tibial component is a porous coated chrome-cobalt sintered bead surface for uncemented use. The porous coating is thicker than a single beads layer. The group studied with peri-apatite coating is an additional solution precipitated calcium phosphated coating, 10-20 μm thick, which coats in between the sintered beads. This coating has been proved to improve the gap healing. This gap has been shown to be quite large in primary reconstructions [[name], 1994 #1131].
- d) Triathlon Cruciate Retaining design.
- e) Triathlon Cruciate Retaining design.
- f) Triathlon Cruciate Retaining and Triathlon Mobile Bearing, Cruciate Retaining design.
- g) Triathlon Cruciate Retaining cemented version with short keel and Triathlon Cruciate Retaining cemented version with standard keel

h) Triathlon Cruciate Retaining cemented version and Triathlon Cruciate Retaining with PeriApatite (uncemented version)

8. Methods

8.1 Study design

The study is a prospective, randomised single centre trial with 25 patients in each group. The patients will be randomly allocated to one of two equally sized groups in each sub-study regarding different treatments and prosthesis designs.

8.2 Operative procedure

All patients will be operated at the Department of Orthopaedics in Hässleholm. The surgeries will be performed using the appropriate guide instruments and according to the surgical-technique manual supplied with the knee system. All femoral and tibial prosthetic components will be inserted according the protocol.

8.3 Randomisation procedure

The randomisation of the patients will take place when the surgeon decides that the patient can be included. The randomisation will be performed by opening a sealed envelope with 25 patients allocated to each group.

8.4 Post-operative mobilisation

Mobilisation will take place according to the ordinary clinical routines at the department of Orthopaedics in Hässleholm. Full weight-bearing is allowed postoperatively. The postoperative care and the mobilisation will be similar for all sub-groups.

8.5 Follow-up

The study period will be two years. Follow-ups will be performed at postoperatively, at 12 weeks and at 1- and 2 years. All assessment variables will be compiled preoperatively and at each follow-up. The patients will be followed indefinitely at 3 years intervals after completion of this protocol.

9. Assessment

Primary assessment variables will be

1. Roentgen stereophotogrammetric analysis (RSA) (Selvik, 1974).

Secondary assessment variables will be

2. Plain radiographs will be obtained for disease classification.
3. Clinical assessment according to the Knee Society Score (KSS) and KOOS score
4. At the post-op follow-up all plain radiographs will be obtained for the assessment of the component position. At the yearly radiographic follow up a weight-bearing investigation will be performed to assess wear, radiolucent zones and stress resorption. A patella sky view projection will be included in the postoperative x-ray and at the yearly controls

10. RSA

All cases will be prepared for RSA investigation by insertion of tantalum markers in the tibial polyethylene component and in the tibial metaphysis (Ryd, 1986).

11. Data analysis

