goal with this sub study is to compare the stability of the fixation when using two different types of Triathlon un-cemented prosthesis designs. PA (HA-surface) versus Pressfit.

d) Triathlon implanted through computer assisted surgery versus conventional technique: Today's surgical technique within knee-arthroplasty has improved greatly with better instruments and more sophisticated equipment e.g. computer assisted surgery. The goal with this sub study is to evaluate if there are any advantages with computer assisted surgery together with Triathlon. The Triathlon knee system has been developed with instrumentation specifically prepared for computer assisted surgery.

e) Triathlon knee prosthesis implanted with MIS technique versus conventional technique: Today's surgical technique within knee arthroplasty is evolving towards smaller incisions and less traumatising techniques, so called Minimal Invasive Surgery (MIS). The goal with this sub study is to evaluate the advantages for the patient when using Triathlon-MIS-technique versus conventional surgical technique.

f) Triathlon Fixed versus Triathlon Mobile Bearing: This sub study is aimed to evaluate if Triathlon mobile bearing will give the patient any advantages over the Triathlon fixed bearing.

g) Triathlon Cruciate Retaining knee (CR) with a tibial keel of standard length randomised against Triathlon Cruciate Retaining knee (CR) with a tibial part with a short keel, both system will be used with cemented fixation. The short tibial keel is thought to facilitate the surgery due to easier access and better positioning possibilities. This sub-study is aimed at evaluating if the short tibial keel will have equal fixation and migration properties as the standard keel.

h) Triathlon Cruciate Retaining knee with cemented fixation randomised versus Triathlon Cruciated Retaining knee with uncemented fixation (Peri-Apatite). The aim with this sub study is to evaluate the uncemented PA knee fixation and migration properties versus the cemented version.

6. Inclusion and Exclusion criteria

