11.2 Statistical analysis

All variable are considered continuous and measured on an interval scale, except migratory pattern, which is proportional. The difference between the two treatment groups will be evaluated with analysis of variance (ANOVA) for continuous variables at different time periods. Clinical scores will also be analysed using the analysis of covariance (ANCOVA) to compensate for different preoperative starting values. Continuous data which are not normally distributed will be analysed by non-parametric ranking tests and proportional values will be analysed by the chi-square test or the Fischer's exact test at low response frequencies.

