The Triathlon RSA study that is conducted in the orthopaedic clinic at Hässleholm's hospital have aimed at studying prosthesis fixation using accurate measuring techniques, so-called X-ray stereo photogrammetric technique (RSA). This method studies micro-motion of a prosthesis component in relation to the bone. All prosthetic components, cemented and uncemented have shown a micro mobility which later can be related to possible future prosthesis loosening. Thus it is of great importance to investigate the long term fixation of the Triathlon prosthesis and to present scientific results confirming that the prosthesis have excellent survival rate when implanted in patients. To reveal all possible aspects of the Triathlon prosthesis the Triathlon RSA study consists of a clinical and a radiographic part, including roentgen stereophotogrammetric analysis (RSA) of the knee prosthesis.

Examination procedure

The Triathlon RSA study was designed to evaluate the Triathlon knee system and to follow patients during the first two years after surgery. As the collected results are very promising and the study has a high scientific value it has been decided to extend the follow-up evaluation period and include a patient visit 5, 7 and 10 years after surgery to the original study design. Primary assessment variables will be similar as to the original study design:

1. Roentgen stereophotogrammetric analysis (RSA) (Selvik, 1974).

Secondary assessment variables will be:

2. Plain radiographs will be obtained for disease classification.

3. Clinical assessment according to the Knee Society Score (KSS), KOOS and EQ-5D score.

Data collection will be done by clinical evaluation, x-rays and patient evaluations collected in a separate folder at the clinic. Data is collected and processed by the research unit at the orthopaedic clinic in Hässleholm. The examinations will be conducted in the same manner as those already performed 1 and 2 years after surgery. During the patient visits an assessment of the knee function will be conducted (KSS) as well as answering patient questionnaires (EQ-5D, KOOS). The patient follow-ups will take place at the clinic in Hässleholm including RSA (stereophotogrammetric analyse) 5, 7 and 10 years after surgery.

Primary objective

To compare the clinical outcomes and long-term implant survival using RSA data including patient opinions about the function and quality of life after knee replacement surgery using the Triathlon knee prosthesis.

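### If sub-study f (fixed versus mobile bearing) is run, a between-arm difference in insert-marker RSA may reflect bearing position rather than fixation, and section 10 states no tray reference

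*Combined protocol and SAP*

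**What the plan says.** - **Markers.** Section 10 reads: "All cases will be prepared for RSA investigation by insertion of tantalum markers in the tibial polyethylene component and in the tibial metaphysis". No section adds a tray marker, a tray-based reading or a separate scheme for any sub-study.
- **The comparison in f.** Section 7 lists the implants: "f) Triathlon Cruciate Retaining and Triathlon Mobile Bearing, Cruciate Retaining design". Section 5 gives the aim: "This sub study is aimed to evaluate if Triathlon mobile bearing will give the patient any advantages over the Triathlon fixed bearing".
- **Role of RSA.** Section 5 makes RSA the principal parameter and includes it in every sub-study; section 9 lists it as the primary assessment variable. The 2014 addendum's Introduction says the RSA work was meant to "have aimed at studying prosthesis fixation using accurate measuring techniques" and adds: "This method studies micro-motion of a prosthesis component in relation to the bone". It does not name the component. The addendum's primary objective is "To compare the clinical outcomes and long-term implant survival using RSA data", together with patient-reported function and quality of life.
- **Clinical outcomes.** Section 9 lists as secondary "Clinical assessment according to the Knee Society Score (KSS) and KOOS score".
- **Tray and insert.** Section 7 describes a chrome-cobalt tibial tray in every prosthesis, so the tray is a different part from the marked polyethylene. The Introduction (section 1) says the locking mechanism is intended to lessen insert micromotion on the tray.
- **Which sub-studies.** Section 5 describes eight (a to h). Section 3 and Amendment No. 2 both count six. Neither says which six.

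**The concern.** RSA tells us about fixation when the marked part moves with the part that is fixed to bone. In f the randomised factor is the bearing, and the bearing carries the prosthesis-side markers. If the mobile insert changes position on its tray between two examinations, the measured motion is tray-on-bone motion combined with insert-on-tray motion, and the second term may be larger in one arm than in the other.

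Randomisation does not remove such a term, because it belongs to the treatment. Nor do larger groups; they make it easier to declare significant. It could suggest poorer fixation of the mobile design when the trays are equally stable, or hide a real fixation advantage. That result would then enter the addendum's reading of RSA as evidence on long-term implant survival. The plan as written has no means of separating the two motions, so it could not show that the effect is small.

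**Working it through.** **1. The plan's own figures.** Section 11.1 assumes MTPM of 1.0 ± 0.5 mm falling to 0.5 ± 0.5 mm, a standardised difference of 0.5/0.5 = 1. A two-sample t-test at two-sided 0.05 and 80% power needs 16.7 per group, so the stated 17 reproduces. Continuous migration of 50% versus 10% needs 25 per group with a continuity correction, also as stated. Neither figure is disputed. The yardstick used below is the planned difference of 0.5 mm.

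**2. Rotation needed to matter.** Assumption, not in the documents: the insert rotates about a vertical axis and the outer marker lies r = 20 to 35 mm from it. Marker displacement is d = 2r·sin(θ/2).

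- At θ = 1 degree: 2 × 20 × sin(0.5°) = 0.35 mm; 2 × 35 × sin(0.5°) = 0.61 mm.
- For d = 0.5 mm, θ = 2·arcsin(d/2r): 1.43 degrees at 20 mm; 0.82 degrees at 35 mm.

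**3. False-significant rate for MTPM.** Simulation inputs:

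- From section 11.1: tray-based MTPM of mean 1.0 mm and SD 0.5 mm, the same in both arms; alpha 0.05, taken as two-sided.
- From section 3: 25 per arm.
- Assumed: tray translation in a random direction with gamma-distributed magnitude; six markers at radius r; MTPM as the largest marker displacement; tray rotation N(0, t) in both arms, with translation recalibrated so that MTPM stays at 1.0 ± 0.5 mm; additional bearing rotation N(0, s) in the mobile arm only. Total rotation SD in the mobile arm is therefore √(t² + s²).
- Test: two-group ANOVA, equivalent to the t-test.

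Percentage of trials declared significant although tray migration is equal (20 mm / 35 mm):

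| Bearing-rotation SD s | t = 0 | t = 0.25° | t = 0.5° |
|---|---|---|---|
| 0.25° | 7 / 10 | 5 / 6 | 5 / 5 |
| 0.5° | 12 / 28 | 8 / 15 | 6–7 / 10 |
| 1° | 35 / 75 | 24 / 57 | 17 / 41 |

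Values move by about one percentage point between repeat runs. With no bearing rotation the rate is about 5%. At s = 0.1 degrees and t = 0 it is 5–6%, which is negligible.

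Tray rotation lowers the rates because the bearing then adds less to the total. With t = 0.5 and s = 0.25, the rotation SD rises only from 0.5 to √(0.25 + 0.0625) = 0.56 degrees.

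**4. Sensitivity, with t = 0.**

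- At 30 per arm (Amendment No. 2) and s = 1 degree the rates are 41% / 82%, higher than at 25.
- Section 11.2 says "Continuous data which are not normally distributed will be analysed by non-parametric ranking tests". A rank-sum test at 25 per arm gives 38% / 77% at 1 degree, so changing the test does not help.
- The rise in mean MTPM is 0.05 / 0.10 mm at 0.25 degrees, 0.11 / 0.20 mm at 0.5 degrees and 0.23 / 0.42 mm at 1 degree.

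Continuous migration between years 1 and 2 was not simulated. The same mechanism could affect it, but no size is claimed.

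**The case against.** Several points on the other side stand.

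- **Two conditions are not documented.** It is not stated that f is one of the six, and the documents describe neither how the mobile bearing moves nor how the limb is positioned at RSA. A reader might infer that an insert-based difference in f cannot be read as fixation at all. That is too strong: if the bearing returns to nearly the same position at each examination, the effect is negligible.
- **Section 10 describes marker placement, not the analysis.** It does not say that the insert is the only part analysed, and a tray-based reading of the same films would not contradict it. One cannot infer that the plan rules out a tray reference, only that none is stated. The method cited there could not be consulted.
- **The fixed arm is not free of bearing motion.** A reader might take the extra motion to exist in the mobile arm alone. The Introduction speaks of reducing insert-on-tray micromotion in the locked design, not of abolishing it. The arms may differ in degree, and neither amount is given.
- **The largest percentages depend on trays that never rotate.** Allowing tray rotation roughly halves the rates at 1 degree, and at 0.25 degrees brings them close to nominal.
- **The stated aim of f is patient advantage**, whereas c, g and h name fixation. KSS and KOOS are unaffected, so it would be wrong to infer that f as a whole is compromised.

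These points limit the strength and size of the concern but do not dispose of it. RSA is still the principal parameter in f and is presented as a fixation measure, and the marked part is the one whose design is randomised.

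**Conclusion.** The point holds in conditional form. If f is run, and if the mobile insert can move on its tray between examinations, a between-arm difference in insert-based MTPM or continuous migration may reflect bearing position rather than fixation, and the plan as written cannot tell the two apart. The size is unknown from the documents. Over the assumed ranges in the table, the false-significant rate for MTPM runs from about nominal (5–10% at a bearing-rotation SD of 0.25 degrees) through 7–28% at 0.5 degrees to 17–75% at 1 degree. These figures are illustrations, not estimates for this implant, because nothing in the documents places f within that range. The issue is confined to the RSA endpoint of one sub-study. It should be fixed, since RSA is the principal parameter and the minimum remedy is a short statement on interpretation.

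**What to change.** 1. State whether f is one of the six sub-studies. If it is not, nothing further is needed on this point.
2. If it is, add to section 10, for example: *In sub-study f, insert-based MTPM and continuous migration are not interpreted as a difference in fixation or implant survival. Conclusions on the aim of f rest on KSS and KOOS.*
3. Where a tray-based reading of the existing stereo radiographs is feasible in both arms, use tray-on-bone migration as the fixation measure in f and report insert-on-tray motion separately. Use the same reading in both arms, and settle feasibility before the arms are compared.

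**Cost.** No extra patients or visits. Where no tray reading is possible, f loses its fixation conclusion. Where it is possible, f bears the extra reading work and possibly lower precision than insert markers give. The documents do not show whether tray models can be obtained or whether existing films suffice, so step 3 should not be assumed to be cheap; step 2 is.

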11.1 Power - statistical considerations

From previous studies the migration during the first two years for cemented prostheses has been about 1.0 ± 0.5 mm (MTPM). Suppose this migration will decrease by 50% to 0.5 ± 0.5 mm. Considering an alpha level of 0.05 and a beta level of 0,20 (power \approx 80%) this will require 17 cases in each group. With a β of 0,75, 15 patients in each group will be needed. Continuous migration between the 1st and 2nd year follow-up has been found in up to 50% of the cases. Suppose that an improvement will have to yield a decrease in continuous migration to 10% in order to be clinic relevant. An alpha level of 0,05 and beta level of 0,20 (power = 80 %) would require 25 cases in each group.

11.2 Statistical analysis

All variable are considered continuous and measured on an interval scale, except migratory pattern, which is proportional. The difference between the two treatment groups will be evaluated with analysis of variance (ANOVA) for continuous variables at different time periods. Clinical scores will also be analysed using the analysis of covariance (ANCOVA) to compensate for different preoperative starting values. Continuous data which are not normally distributed will be analysed by non-parametric ranking tests and proportional values will be analysed by the chi-square test or the Fischer's exact test at low response frequencies.

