This is a prospective, comparative, randomised single centre clinical study. The Triathlon and the Duracon Knee Systems have to be implanted for evaluation in this study. Patients will be randomised to one of two equally sized groups within each sub study. Both knee systems are commercially available. Patellae will be resurfaced if needed. All patients included in the study will meet all inclusion criterias and none of the exclusion criterias.

Ethic Committee approval for the study will be obtained by the investigator prior to starting the inclusion of patients in the study.

Patients will be considered for enrolment according to the clinical findings and subject to gaining their suitable written informed consent (see Appendix II).

The principal evaluation parameter will be the RSA. Patient outcome will be assessed by the KOOS questionnaire and the KSS. Clinical evaluation will include the chair raise test, measurement of the extension strength, and a patella evaluation. The evaluation of the Triathlon system will be carried out in several steps, described as sub-studies all including RSA-technique.

Sub-studies:

a) Triathlon versus Duracon: The Triathlon system has a heritage in the well documented Duracon system, which has shown very good results in the Swedish Knee Register. The goal with this study is to get an indication of the long-term results of Triathlon. The evaluation is carried out by a prospective randomised RSA-study with Triathlon cemented knee prosthesis versus Duracon cemented knee prosthesis

b) Triathlon Cruciate Retaining (CR) versus Triathlon Posterior Stabilized (PS): During knee prosthesis surgery the surgeon many times need to make a judgement on if to keep a defect anatomical structure or if to replace it with knee prosthesis with a design that allows for adjustment of this defect. This sub study is aimed to evaluate which prosthetic choice to be made in respect of stability, long-term results and patient outcome.

c) Triathlon PA (HA-surface) versus Triathlon Pressfit design: The goal with the uncemented technique is to reach a full integration between the bone and the prosthesis. During the last years the usage of prosthesis with hydroxyapatite surface within tooth-, mandibular-surgery, hips- and knee-joints, have increased significantly. It has been shown that a thin layer of hydroxyapatite stimulates the anchorage of the implant. The

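### RSA is primary, but the plan sizes two RSA endpoints at a full 0.05 each and never says which one decides a sub-study

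*Combined protocol and SAP*

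**What the plan says.** Section 5 states: "The principal evaluation parameter will be the RSA". Section 9 lists RSA as the sole primary assessment variable, and the 2014 addendum (Examination procedure) keeps it. None of these names a parameter or a time point.

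Section 11.1 sizes two quantities derived from RSA.

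- **Two-year MTPM.** The starting point is that "the migration during the first two years for cemented prostheses has been about" 1.0 mm with SD 0.5, to be halved to 0.5 mm. "Considering an alpha level of 0.05 and a beta level of 0,20", it arrives at 17 per group.
- **Continuous migration between years 1 and 2.** This is put at no more than 50% historically. "Suppose that an improvement will have to yield a decrease in continuous migration to 10% in order to be clinic relevant". Then: "An alpha level of 0,05 and beta level of 0,20 (power = 80 %) would require 25 cases in each group".

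Section 11.2 says "The difference between the two treatment groups will be evaluated with analysis of variance (ANOVA) for continuous variables at different time periods", and that "proportional values will be analysed by the chi-square test", or by Fisher's exact test when responses are few. RSA is scheduled before discharge, at 3 months, 1 year and 2 years, and under the addendum also at 5, 7 and 10 years. Amendment No. 2 raises the group size from 25 to 30 without linking it to either endpoint.

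**The concern.** RSA yields several endpoints, and two of them have been given their own hypothesis and their own 5% error rate. The plan does not say that one decides, that they are tested in order, that alpha is shared, or that both must succeed.

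Two things follow. First, MTPM and continuous migration can disagree within a sub-study, and nothing settles which answer is the result. That holds whatever the error rate is. Second, an author who followed the plan could present either endpoint, or a favourable visit, as the primary finding at 5%.

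Sub-study g is a special case. It asks whether the short keel fixes and migrates the same as the standard keel, yet section 11.2 offers only tests for a difference. A non-significant difference test does not show sameness.

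**Working it through.** **1. Reproduce the plan's sizes (two-sided 0.05, power 80%).** Inputs are from section 11.1.

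MTPM, difference 0.5 mm, SD 0.5 mm: n = 2(1.960 + 0.842)² × (0.5/0.5)² = 15.7, or 16 by the normal formula. The t-test solution is 16.7, so 17 per group, as stated.

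Continuous migration, 50% vs 10%, mean rate 0.30:

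- Uncorrected: n = [1.960√(2 × 0.30 × 0.70) + 0.842√(0.25 + 0.09)]² / 0.40² = 19.4, so 20.
- Continuity-corrected: (n/4)[1 + √(1 + 4/(0.40n))]² = 24.1, so 25 per group, as stated.

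Both stated sizes therefore spend a full two-sided 0.05. The arithmetic is sound; what is missing is the decision rule.

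**2. False-positive chance if any one significant result counts.** Two independent tests of exact size 0.05 would give 1 − 0.95² = 0.0975. Fisher's test is conservative: its exact size at 25 per group and a 30% event rate is 0.023 (0.022 for corrected chi-square). So a rough check is 1 − 0.95 × 0.977 = 0.072.

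Simulation under no difference used 40,000 runs per setting, normal data, equal correlation between three visits, a t-test per visit, and an event defined as a year 1 to year 2 change above a cut giving a 30% rate. The correlation, the event rate and normality are assumptions; the documents give none of them. Binary endpoint by Fisher:

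| Tests that could win | n per group | correlation 0.7 | correlation 0.9 |
|---|---|---|---|
| Two-year MTPM + continuous migration | 25 | 0.072 | 0.072 |
| | 30 | 0.073 | 0.074 |
| Plus 3-month and 1-year MTPM | 25 | 0.130 | 0.104 |
| | 30 | 0.132 | 0.107 |

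Corrected chi-square gives practically the same values. With event rates of 10-50% the ranges are 0.056-0.083 and 0.092-0.134. Uncorrected chi-square gives about 0.10 for the two sized endpoints (0.095-0.102), but part of that is the test's own size (0.054 at 25 per group and a 30% rate).

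**3. Power if one endpoint is named (no losses).**

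| Endpoint and assumption | 25 per group | 30 per group |
|---|---|---|
| Continuous migration, Fisher, 50% vs 10% | 0.833 | 0.914 |
| Continuous migration, Fisher, 40% vs 10% | 0.591 | 0.705 |
| MTPM, t-test, 1.0 vs 0.5 mm, SD 0.5 | 0.934 | 0.968 |

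The 40% row matters because section 11.1 gives 50% as a ceiling. The MTPM inputs are for cemented prostheses. Sub-study c sets out to "compare the stability of the fixation when using two different types of Triathlon un-cemented prosthesis designs", and one arm of h is uncemented, so MTPM power is not shown for either. Nor is it shown for b, d, e and f, whose fixation is not stated.

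**4. Precision for sub-study g.** The 95% confidence interval half-width for the MTPM difference is t × SD × √(2/n). If SD is 0.5 mm:

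- 25 per group: 2.011 × 0.5 × √(2/25) = 0.284 mm.
- 30 per group: 2.002 × 0.5 × √(2/30) = 0.258 mm.

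**The case against.** The best defence is that the deciding endpoint can be inferred. Continuous migration is the only calculation that yields the planned 25 per group, and the only one tied to clinical relevance. The inference is reasonable, and it is why that endpoint is the natural default. But no section calls it primary, and taking the larger of two sizes is also what one does to cover both endpoints. Even on this reading no cut-off for continuous migration is given, and the choice between chi-square and Fisher depends on an undefined low frequency.

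A second defence is that the inflation is conditional and modest. This stands. If both endpoints had to succeed there would be no inflation. The 10-13% figure also needs formal MTPM tests at three visits, and section 11.2 does not list visits; that is a reading of the RSA schedule.

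Third, one RSA test does not fit every aim. Sub-studies e and f ask about advantage to the patient, b includes patient outcome, and the addendum has its own long-term primary objective, which covers clinical outcomes and patient opinion as well as RSA. This also stands, and the fix has to respect it.

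A reader might go further and infer that the plan accepts any single significant result, so that its true error rate is 10% or more, or that an endpoint was picked after results were seen. The documents support neither. No rule of that kind is stated. The addendum does call the collected results promising, but it does not say which endpoints or sub-studies had been examined.

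**Conclusion.** The concern holds as a missing decision rule for the primary RSA comparison. The ambiguity about which endpoint counts rests on the text alone and needs no assumption. The error rate is conditional: if any one significant result counts, about 7% per sub-study for the two sized endpoints with Fisher or corrected chi-square, and about 10-13% with the two earlier MTPM visits added, under normal data, between-visit correlation 0.7-0.9 and a 30% event rate.

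It would be wrong to conclude that the trial is undersized on its own terms, since both stated sizes reproduce. The power margin for continuous migration is thin, however, if the control rate lies below the 50% ceiling. For sub-study g the plan has no analysis that answers the question asked.

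**What to change.** In section 11.2:

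- For the two-year analysis of each sub-study that asks about a difference in fixation, name one deciding RSA test at two-sided 5%. The default is continuous migration in years 1 to 2 by Fisher's exact test, with its cut-off stated.
- Report two-year MTPM as key secondary with estimate and 95% confidence interval, and the 3-month and 1-year results as supportive.
- Where a sub-study's RSA data have already been seen, state that the choice is post hoc and does not restore the 5% level.
- For sub-study g, do not let a difference test decide. Report the 95% confidence interval for the MTPM difference and state that non-significance is not evidence of equal fixation.
- For sub-studies b, e and f, state that the RSA test decides fixation only.

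In the addendum, say that the 5, 7 and 10 year RSA results serve its own long-term objective and are not further chances to win the two-year comparison.

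The cost is wording, with no extra patients or visits. Under the plan's assumptions and without losses, the default keeps 83% power at 25 and 91% at 30 per group; at 40% vs 10% this falls to 59% and about 70%, which should be disclosed. The real price is that MTPM and the other visits can no longer be claimed as the primary two-year result.
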